MPX was shown to be a safe therapy. However, the overall results have been disappointing but there have been a few people with responses to therapy. This led to the hypothesis that there may be a subset of patients, who can be identified early on, who would benefit from therapy. A previous study showed that in patients with a variant of the manganese superoxide dismutase gene (SOD2), baseline exposure to antioxidants significantly influences the risk of developing prostate cancer. Manganese superoxide dismutase (MnSOD) is encoded by the SOD2 gene and is one of the major enzymes responsible for detoxification of reactive oxygen species in mitochondria. A mutation at the -9 position results in a change from valine to alanine and alters the structure of the protein. This mutation (AA), present in about 25% of prostate cancers, was shown in an observational study that men who had the alanine/alanine genotype and high antioxidant levels had much lower rates of all prostate cancer and clinical aggressive prostate cancer.

Another antioxidant and natural product, pomegranate, has also been studied in the setting of biochemical recurrent prostate cancer. With pomegranate, there were similar findings as above in the MPX trials of no significant change in PSADT in those taking the supplement compared to those on placebo. However, those patients with AA genotype of SOD2 gene did have a significant benefit, with a 12 month increase in PSADT ( $p=0.03$ , from 13.6 months at baseline to 25.6 months at follow up) compared to only a 1.8 month change in the placebo group (10.9 months at baseline to 12.7 months at baseline).

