**8-OHdG** – 8-hydroxy-2’deoxyguanosine is a form of damaged DNA caused by excess free radicals and is a marker of DNA oxidation which can be measured in the urine. At baseline, men with prostate cancer have an intermediate level of 8-OHdG detected in urine which was shown to be transiently increased after radiation therapy in a small study of seven men. Urinary levels were shown to be decreased in men who were treated in a trial of antioxidants with selenium-enriched yeast. Serum levels were shown in one study of 32 men with localized prostate cancer to be decreased following dietary intervention with lycopene. Prostatic tissue levels of 8-OHdG were not significantly decreased in a neo-adjuvant trial of 70 men randomized to pomegranate extract or placebo. In our population, we hypothesize 8-OHdG will be decreased in those being treated with MPX compared to placebo, and will correlate with response to treatment.

**Malondialdehyde (MDA)** – Malondialdehyde is a byproduct of lipid oxidative degradation and is the most commonly used correlative study to measure oxidative stress in prostate cancer patients. There have been mostly consistent results within the published literature with one study showing no difference between levels in patients with metastatic castration resistant prostate cancer compared to controls but most cross sectional studies showed higher levels of MDA in those with prostate cancer compared to controls. One study showed a correlation between PSA and levels of MDA but not with vitamin antioxidants. Another study also showed increased risk of disease progression with higher levels of MDA. Due to the frequency and consistency of the results, we think it is reasonable to include this in our correlative analysis.

However, there are pitfalls to the measurement some variability based on the method used to measure MDA and it is highly bound in serum.

*Additional oxidative correlatives that will be stored and analyzed if sufficient funding allows.*

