**Superoxide dismutase activity** - Superoxide dismutase is a ubiquitous enzyme that converts oxygen free radicals to hydrogen peroxide and oxygen. In humans there are 3 forms, SOD1 found in cytoplasm, SOD2 found in mitochondria and SOD3 found extracellularly. SOD1 and SOD2 activity, defined as the amount of enzyme needed to exhibit 50% dismutation of the superoxide radical, can be generated separately from a serum sample. Baseline levels of SOD activity in the study population (AA genotype) will be compared to men in the screened population to determine if genotype influences phenotype of activity levels. It has been previously shown polymorphisms in MnSOD (SOD2) gene are not associated with increased risk of prostate cancer. However, there are strong correlations between genotype, baseline exposure to anti-oxidant status and response to treatment with antioxidants. Additionally, higher levels of SOD have been found in prostate cancer patients compared to controls.

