## **5. TREATMENT PLAN**

This is a randomized, double-blind, placebo controlled multicenter study to compare the change in slope and PSADT from baseline between placebo and MDX treatment groups. Approximately 500 subjects will be registered and genotyped to find 80 men with AA genotype for enrollment.

Those with AA genotype will be enrolled and randomized 1:1 (40 to placebo and 40 to MPX). Treatment on study will last 48 weeks and will be administered on an outpatient basis.

Appropriate dose delays and discontinuation recommendations for MPX are described in Section 6. Adverse event reporting requirements and potential risks are described in Section 7. No investigational or commercial agents or therapies other than those described below may be administered with the intent to treat the patient's malignancy.

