 **Primary discontinuation reason and sampling:** If patient leaves the study for any reason prior to 24 weeks but > 12 weeks on trial, please record whether DC reason was patient meeting protocol defined progression (defined in Sec. 5.4 of this protocol) or DC reason was investigator judgement. If reason was protocol-defined progression, record whether there was pain, metastases on bone or CT scan and/or PSA progression. Also collect serum and urine for correlative studies, and perform CT and bone scans unless scans and patient samples have been collected in the past 8 weeks.

 **Pre-trial PSA's:** It is important to have 3 pre-trial PSA values (please refer to inclusion criteria #3 and #4) prior to day 0 and to collect a day 0 PSA value for on-study calculations.

 **Serum correlative samples:** One tube at original screening of 500 patients; three tubes at baseline, 12 weeks, 24 weeks, 36 weeks, 48 weeks and progression for patients on MAP trial.

 With **medical history** record prior prostatectomy, prior radiation (brachytherapy, SBRT, etc.) plus start and end dates of any prior hormonal therapy including name of drug. Please also state alcohol and smoking intake.

 **Open label extension:** For patients discharged prior to 48 weeks, open label MPX drug will be offered only to patients who meet protocol defined progression per Section 5.4, patients with radiographic progression (metastatic disease) are excluded.

 **MnSOD2 sample:** All 500 patients should get genotype (5ml blood).

 **Comprehensive metabolic panel** to include measurement of sodium, potassium, chloride, bicarbonate, BUN, creatinine, glucose, total bilirubin, calcium, total protein, albumin, AST, ALT, and alkaline phosphatase

 **Brief physical examination** includes cardiovascular, pulmonary, abdominal and Symptom-directed; includes investigating any new abnormalities and weight. Interval history includes any hospitalizations, illnesses, changes in medication

 **Eligibility:** All inclusion/exclusion criteria should be assessed at screening and confirmed prior to randomization

 **Drug compliance:** Compliance will be assessed by reviewing both returned # of pills and pill diary

 **Follow-up Visit:** The last visit will be 28 days (± 3 days) following last dose of study drug.

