**Sample size and accrual:** This two arm randomized study will determine if there are differences in the change in PSA slope (post supplementation minus pre supplementation) between patients supplementing with MPX (Arm A) and patients that are not (Arm B). The accrual rate for each site is expected to be 1 patient per month. With 16 to 17 sites, is expected that we could accrue 500 patients over 4 years, for which we will have baseline MnSOD genotype and baseline antioxidant status, of which approximately 80 would be of the required AA genotype and eligible for randomization to MPX or placebo. Overall the study would take 4 years of accrual and another year for follow-up. PSA slope will be defined by the linear regression line of the natural log of PSA (in ng/mL) against time (in months). The primary statistical analysis will be an analysis of covariance (ANCOVA) to compare the two arms at the final analysis, adjusting for baseline PSA slope. Implications of the sample size are given based on simulations which include a single interim analysis for futility midway through the trial. The predictive probability approach for the futility analysis is described in the interim analysis section below. Based on the previous study of MPX at Hopkins, we conservatively estimate that the difference in the post-treatment PSA slope (MPX minus placebo), adjusting for pre-treatment PSA, in this group of patients with the AA genotype will be -0.05 with the MPX arm having lower post-treatment slopes (MPX slope 0.033 ng/mL/month versus untreated 0.083 ng/mL/month). Patients with the AA genotype will be randomized to MPX (Arm A) and placebo (Arm B) in a 1:1 ratio. Using a two sided 5% type I error allowance, a sample size of 78 (39 per arm), and minimal correlation between the pre and post treatment PSA slopes, this study will have 83% power to detect a difference in post-study PSA slope of -0.05. Use of the ANCOVA design with covariate adjustment for pre-treatment PSA slope will tend to increase the power depending on the level of the correlation between paired PSA slope measurements (i.e., pre- and post-treatment). As an example, for a correlation ( $\rho$ ) of 0.30, the power would increase to 87%.

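### The exploratory SOD-activity comparison is meant to test genotype, but its groups are defined by enrolment; grouping all genotyped men as AA or non-AA on one screening sample would answer the question asked

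*Combined protocol and SAP*

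**What the plan says.** Section 2.4.2 places superoxide dismutase (SOD) activity under a heading that makes it conditional: "Additional oxidative correlatives that will be stored and analyzed if sufficient funding allows". The planned analysis is one sentence: "Baseline levels of SOD activity in the study population (AA genotype) will be compared to men in the screened population", with the aim "to determine if genotype influences phenotype of activity levels". Section 11.3 lists no method, test or groups for it, and Section 1.3 does not name it as an objective.

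On who is sampled and when:

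- Section 5: "Approximately 500 subjects will be registered and genotyped to find 80 men with AA genotype for enrollment". Study Calendar footnote 8 likewise asks for a genotype on all 500 men.
- Study Calendar footnote 5, on serum: "One tube at original screening of 500 patients; three tubes at baseline" and later visits for men on the trial.
- Section 9.2 draws the randomised men's first serum at Day 0 before dosing, for antioxidants and malondialdehyde; it does not mention SOD.
- Section 4.1 registers eligible AA men after pre-screening. The Study Calendar puts genotyping in the pre-screen column and the eligibility check in the next one.
- Section 11 describes the randomised men by two conditions: "approximately 80 would be of the required AA genotype and eligible for randomization".

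**The concern.** A question about genotype needs groups that differ by genotype and otherwise as little as possible. Here one group is AA men who went on to be enrolled, and the other is whoever was screened. Three things follow.

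1. **Eligibility is mixed with genotype.** Sections 3.1 and 3.2 filter on organ function, stable supplement use for 2 months, no Muscadine Plus for 2 months, recent high-dose steroids or cancer treatment, and metastases. Some of these bear on antioxidant exposure, which Section 2.4.2 itself links to genotype and treatment response. Only the enrolled side has been through them.
2. **AA men may sit on both sides.** Nothing limits the comparator to non-AA men. AA men who were genotyped but not randomised would dilute the contrast.
3. **The draws may differ in time,** if the enrolled men's value comes from Day 0 and the comparator's from original screening.

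At stake is whether a difference, or the lack of one, can be attributed to genotype. No randomised comparison is affected.

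**Working it through.** The plan gives no effect size, SD, alpha or power for this comparison, so there is no figure to reproduce.

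**Inputs.** Genotyped: 500 (Section 5). Randomised AA men: 80 (Sections 5 and 11). AA prevalence *p*: Section 2.2.3 says AA is "present in about 25% of prostate cancers", and its phase II counts agree, (4 + 8 + 11)/91 = 23/91 = 25.3%. The accrual plan itself implies no more than 80/500 = 16% who are both AA and enrolled. I therefore show 16% to 25%.

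**Step 1: AA men left in the comparator.** AA men = 500*p*. Not randomised = 500*p* − 80. If trial men are removed, the comparator's AA share is (500*p* − 80)/420. If the comparator is all 500, its AA share is *p*. The fraction of a true AA versus non-AA difference that survives is 1 minus that share.

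| *p* | AA men | AA, not randomised | AA share of 420 | Difference kept (420) | Difference kept (all 500) |
|---|---|---|---|---|---|
| 16% | 80 | 0 | 0% | 100% | 84% |
| 20% | 100 | 20 | 4.8% | 95.2% | 80% |
| 25% | 125 | 45 | 10.7% | 89.3% | 75% |

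**Step 2: illustrative power.** Assume a genotype difference of *d* SD (my assumption) and a two-sided 5% test. Power ≈ Φ(*k·d*/√(1/n₁ + 1/n₂) − 1.96), where *k* is the fraction kept.

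At *p* = 25% and *d* = 0.3:

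- Literal wording, trial men removed: 80 vs 420, *k* = 0.893. √(1/80 + 1/420) = 0.122; 0.893 × 0.3/0.122 = 2.20; power 59%.
- Comparator read as non-AA men: 80 vs 375, *k* = 1. √(1/80 + 1/375) = 0.123; 0.3/0.123 = 2.44; power 68%.
- Grouped by genotype: 125 vs 375, *k* = 1. √(1/125 + 1/375) = 0.103; 0.3/0.103 = 2.90; power 83%.

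Of the 24-point gap, about 9 points come from AA men in the comparator and about 15 from not using the 45 unrandomised AA men as AA men. For *d* = 0.2 the first and last figures are 31% and 49%; for *d* = 0.4 they are 83% and 97%. Against all 500 men, treating the overlapping groups as independent, the literal wording gives roughly 46% at *d* = 0.3.

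At *p* = 16% with trial men removed, both versions are 80 vs 420 with *k* = 1: 0.3/0.122 = 2.46, power 69%. The gain is zero.

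**Step 3: eligibility and timing.** The Study Calendar order is genotype, then eligibility, then Day 0. An enrolled man has passed all three stages; a man in the wider screened group may have passed only the first. This holds at any prevalence and also if the comparator is non-AA men. The documents give nothing from which to size the bias.

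**The case against.** The best defence is that this is a loose sentence of intent, not an analysis plan. With one side labelled AA and the aim stated as genotype, the authors probably meant AA against the other genotypes. That is fair, and it would remove the contamination. It would not remove the eligibility difference, and it would leave any unrandomised AA men unused.

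The timing point can also be contested. Section 9.2 fixes Day 0 for other assays, and Section 11 uses the word baseline for antioxidant status in all 500 men. Baseline SOD activity could therefore already mean the screening tube for everyone. This stands: the timing difference is conditional.

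Section 3.1 presents its criteria as conditions for registration, and Section 5 speaks of registering all 500, so one could argue that all 500 were eligible. Section 4.1, the calendar columns and calendar footnote 11 point the other way, but the usage is not consistent.

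A reader might infer more than the documents support:

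- **That AA contamination is certain.** It needs a prevalence above 16% or trial men left in the comparator. The counts 125 and 45 appear nowhere in the plan.
- **That the plan gives up 24 points of power.** That figure needs 25% prevalence and an effect of 0.3 SD that the documents do not give.
- **That this is the trial's only check of mechanism.** Section 11.3 lists other mechanistic correlatives. This is only the stated comparison of whether AA genotype alters enzyme activity, and it would not show whether MPX works in AA men.

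**Conclusion.** The point holds as a minor one. The stated groups do not match the stated aim: they are defined by enrolment, so eligibility is mixed with genotype on either reading of the comparator, as long as genotyping precedes the eligibility check as the calendar shows. Loss of contrast from AA men in the comparator is about 11% at 25% prevalence with trial men removed, 25% if the comparator is all 500 men, and nil at 16% with trial men removed. The power figures only illustrate direction, and the time-of-draw difference applies only if baseline means Day 0. The size of the eligibility effect is unknown. The analysis is exploratory and funding-dependent, so the primary endpoint, the randomised comparison and safety are unaffected.

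**What to change.** In Section 2.4.2, state that SOD activity will be compared between AA and non-AA men among all genotyped men, whether or not later randomised, using the original-screening tube for everyone. Keep Day-0 samples for on-study change. Add a line to Section 11.3 naming the groups, the sample and the test. A trend across the three genotypes is optional, since the trial's hypothesis concerns AA men only.

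The cost is small. Genotypes are already planned for all 500 men, and the present sentence already implies assaying serum from screened men. The one dependency is the screening serum tube. It appears only in Study Calendar footnote 5; Section 9.1 lists pre-screen blood for genotyping only, Section 9.2 lists serum from the 80 randomised men, and the calendar's serum row, as extracted, shows no pre-screen mark. These should be reconciled. If the tube is not in fact drawn, there is no screened-population serum and the comparison cannot be done in either form without adding it.

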### 2.4.3 Microbiome

**Microbiome** – An emerging area of interest within oncology is the microbiome and its impact on the effectiveness of therapies. Even with the prostate and the urine, once considered a “sterile” site, there are bacterial organisms that are theorized to contribute to the pathobiology of prostate cancer. There are also differences described between the gut microbiome in men with prostate cancer compared to those without prostate cancer. A natural next question is if the microbiome can be altered in a way to diminish disease progression. There has been some early evidence that intake of another antioxidant, pomegranate, alters the stool microbiome and stimulates the growth of *Akkermansia muciniphila*, a potentially beneficial bacterium that has been associated with increased responsiveness to immunotherapy. In our study, we will characterize the stool microbiome via rectal swab at baseline and 12, 24, 48, 36 and 48 weeks in the randomized patient population to determine whether MPX influences the composition of the gut microbiome.

## 3. Eligibility Criteria

### 3.1 Inclusion Criteria

Patients meeting the following conditions are eligible for registration and participation in the study:

1. Subject has histologically or cytologically confirmed adenocarcinoma of the prostate
2. Subject has undergone definitive treatment (surgery, surgery with radiation therapy, cryotherapy, radiation therapy or brachytherapy) for the primary prostate tumor (prior chemotherapy is not allowed).

- a. A subject with a rising PSA post-prostatectomy should consider radiation as a potentially curative alternative. If subject declines radiation or is not a candidate for radiation, he may be considered eligible in this setting.
3. Subject has a rising PSA on a minimum of 3 time points (2 rises) within the 12 months prior to study initiation (this will include the PSA measurement taken at the screening visit, but not at the baseline day 0 study visit). The three time points must be at least 21 days apart. Note: Fluctuations in PSA are allowed per Bubley et al 1999 working group criteria. 
4. For purposes of calculating PSADT:
  - a) All PSA values used in the calculation should be  $\geq 0.10$  ng/ml and overall should follow a rising trend;
  - b) Record every available PSA drawn within the last 12 months;
  - c) The minimum requirement is 3 PSA values;
  - d) For radiotherapy only patients, record PSA nadir value and collection date.PSADT must be positive according to Memorial Sloan Kettering Cancer Center Prostate Cancer Nomograms under this link:  
<http://www.mskcc.org/applications/nomograms/prostate/PsaDoublingTime.aspx>
5. At least 2 PSA rises need to be after a normal Testosterone for those patients who had prior hormone therapy.
6. One of the following criteria must be met.
  - a. Absolute level of PSA  $>0.2$ ng/mL following surgery. (surgery only)
  - b. Absolute level of PSA  $>0.2$ ng/mL for subjects treated with multiple treatment modalities (e.g., surgery + radiation, surgery + cryotherapy, etc.).
  - c. A rise by 2 ng/mL or more above the nadir PSA will be considered the standard definition for biochemical failure after radiation therapy with or without hormonal therapy. (radiation only)
7. Subject is  $>18$  years of age.
8. Subject has life expectancy of greater than 12 months.
9. Subject has ECOG performance status 0, 1 or 2
10. Subject has testosterone level of  $\geq 150$  ng/dL at screening.
11. Subject has normal organ and marrow function as defined below:
  - a. Leukocytes  $>3,000$ /mcL
  - b. absolute neutrophil count  $>1,500$ /mcL
  - c. platelets  $>100,000$ /mcL
  - d. total bilirubin  $\leq 1.5$  x upper limit of normal except for Gilberts  
 $\leq 2.5$  x upper limit of normal
  - e. AST(SGOT)/ALT(SGPT)  $\leq 2.5$  X upper limit of normal
  - f. creatinine  $\leq 2.5$  upper limit of normal

12. Subject agrees to abstain from other commercially available MuscadinePlus (MP) products (Vinetra, MPlus or MP capsules) while participating in this study.
13. Subject's use of other dietary/herbal supplements (e.g. saw palmetto, selenium, pomegranate juice or pills, acai concentrated extract, etc) has been stable for at least 2 months prior to screening and the subject agrees not to stop or change the dose(s) while participating in the study.
14. Subject has signed a written informed consent document and agrees to comply with requirements of the study.
15. CT or MRI chest/abdomen/pelvis and bone scan without evidence of metastatic disease as an inclusion (Chest X ray may be used instead of Chest CT scan).
16. Subject agrees to genotyping of *MnSOD2* gene. Only those with AA genotype will be randomized.

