As the previous section documents, preclinical studies of muscadine grape skin offer evidence that it may extend the time between biochemical recurrence and development of metastatic disease. While the Phase II study described above found no significant difference in PSA doubling time between placebo and either dose of MPX, there was a signal of benefit in the subgroup analysis of men with the AA genotype that received high dose MPX. It is therefore proposed to test the benefits of high dose MPX in capsule formulation in a randomized, controlled study of men who have failed primary therapy, either radiation, surgery or cryotherapy, as primary treatment for prostate cancer. Eligible subjects will have a rising PSA and will have 3 PSA values at least 21 days apart with a recovered testosterone to be able to calculate a baseline PSA doubling time. The primary endpoint of this study will be mean PSA slope during the study period.

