### **Randomization**

Once eligibility is confirmed, patients will be randomized to a treatment group according to the randomization schedule. Patients will be randomized to receive either placebo or MPX in a 1:1 ratio.

The investigators, study site personnel except designated pharmacy staff, and the subject will remain blinded to each subject's treatment throughout the course of the study.

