6. Calculate the predicted probability of rejecting the null hypothesis at the end of the study.

If interim analysis simulations indicate that the probability of a successful trial would be less than 10%, we will consider stopping the trial for futility. The table below gives the operating characteristics of the monitoring plan based on 2000 simulations for different scenarios, each scenario corresponding to different treatment effects and different levels of correlation between the pre-treatment and post-treatment PSA slope. The seventh row shows results using the hypothesized treatment effect of a mean difference of -0.05 with a standard deviation of 0.075, and minimal correlation. We do expect some correlation between pre and post-treatment values, so power will tend to increase with increasing correlation. The significance level for the final analysis is 0.05. Scenarios 1-3 give operating characteristics under the null (no treatment effect).

**Table 1.** Operating characteristics of monitoring rule from 2000 simulated studies with one interim analysis based on 100 predicted study conclusions and final analysis based on an ANCOVA model. Simulations use a *g*-prior with  $g=39$  (i.e. the sample size at the time of the interim analysis). All simulations assume the standard deviation of post-treatment PSA slope is 0.075.

Scenario	Treatment Effect	Correlation (pre- and post-treatment measures)	Stop for Futility %	Would have stopped for Futility and would have Rejected %	Overall studies rejecting Ho %
1	0.0	0.1	34.0%	0.10%	4.3%
2	0.0	0.2	33.5%	0.35%	5.6%
3	0.0	0.3	34.5%	0.20%	4.4%
4	-0.025	0.1	21.9%	1.00%	31.8%
5	-0.025	0.2	20.4%	0.80%	30.6%
6	-0.025	0.3	17.5%	1.40%	35.0%
7	-0.050	0.1	4.5%	1.25%	82.7%
8	-0.050	0.2	4.4%	0.75%	81.9%

9	-0.050	0.3	3.0%	0.95%	87.3%
10	-0.075	0.1	0.4%	0.30%	98.8%
11	-0.075	0.2	0.4%	0.20%	99.1%
12	-0.075	0.3	0.2%	0.15%	99.7%

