### 11.1 Analysis Plans for Primary Objective

**PSA Slope:** Eligible patients must have a rising PSA with a minimum of 3 time points but up to 17 time points (2 rises at least 21 days apart) within the 12 months prior to study initiation (this could include the PSA measurement taken at the screening visit, but not at the baseline day 0 study visit). The pre-treatment slopes will be calculated based on these data prior to baseline (day 0). A minimum of three time points but up to five time points will be used for calculating on-study slopes: baseline, 12, 24, 36, and 48 week assessments. All data points will be used unless an assessment is unavailable, in which case the remaining time points will be used. There must be a minimum of three data points, and there will be no imputation of missing PSA values.

The primary objective will be based on the intent-to-treat (ITT) population and assessed with an ANCOVA model, with post-treatment PSA slope as the independent variable and study arm and baseline PSA slope as covariates. A two-sided t test at the 0.05 significance level will be used to determine if, adjusting for baseline, the post-treatment PSA slope has been reduced with MPX supplementation (Arm A). Scatterplots of post treatment PSA slope by baseline slope will be used to visualize the fitted ANCOVA model. Boxplots of the observed changes will also be used to visualize the results.

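### The pre-treatment PSA slope rule does not exclude PSAs drawn before testosterone recovered, so in some men with prior hormone therapy it can overstate baseline PSA growth

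*Combined protocol and SAP*

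**What the plan says.** Section 2.3 states the intent: eligible men "will have 3 PSA values at least 21 days apart with a recovered testosterone to be able to calculate a baseline PSA doubling time".

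The operative text is looser.

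- Section 3.1 item 4, on calculating PSADT, has the instruction "Record every available PSA drawn within the last 12 months". It adds that values used must be at least 0.10 ng/ml and follow a rising trend.
- Item 5 adds "At least 2 PSA rises need to be after a normal Testosterone for those patients who had prior hormone therapy". It does not say that values before that testosterone are left out.
- Section 11.1 takes 3 to 17 PSAs from the 12 months before study and says "The pre-treatment slopes will be calculated based on these data prior to baseline (day 0". It states no testosterone condition.

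Testosterone recovery appears in three forms: *recovered* (section 2.3), *normal* with no number (item 5), and at least 150 ng/dL at screening (item 10). The study calendar schedules testosterone at screening only.

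Exclusion 2 attaches a 12-month condition to testosterone-modulating therapy. It can be read as no such therapy in the last 12 months, which is the likely meaning, or as excluding only men treated for at least 12 months.

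The resulting pre-treatment slope has three uses: the PSADT stratum (up to 9 months, or longer), the covariate in the primary ANCOVA, and the denominator of the on-study/pre-treatment PSADT ratio in section 11.2.

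**The concern.** On its likely reading, exclusion 2 removes PSAs drawn on hormone therapy but not PSAs drawn while testosterone was still recovering. The hormone-free period and the PSA window are both 12 months, so the window can open as therapy ends. A PSA that climbs because testosterone is returning passes the rising-trend test, because it rises. Two later rises satisfy item 5, and the earlier values can still enter the regression.

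In such a man the fitted pre-treatment slope mixes testosterone recovery with underlying PSA growth and is too steep. Three things follow. He may be placed in the wrong PSADT stratum. The ANCOVA covariate carries extra noise. His PSADT appears to lengthen on study even if nothing has changed. The last matters most, because section 11.2 plans within-arm paired tests and confidence intervals for change from baseline, and these have no control for it.

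**Working it through.** **1. The plan's power.** Inputs from section 11: 39 per arm, 1:1, two-sided 5%, difference −0.05, and "All simulations assume the standard deviation of post-treatment PSA slope is 0.075". The standard error is 0.075 × √(1−ρ²) × √(2/39).

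| ρ | SE | 0.05/SE | Power, normal | Power, noncentral t (75 df) | Plan |
|---|---|---|---|---|---|
| 0 | 0.0170 | 2.94 | 83.7% | 82.8% | – |
| 0.1 | 0.0169 | 2.96 | 84.1% | 83.2% | 83% (Table 1: 82.7%) |
| 0.3 | 0.0162 | 3.09 | 87.0% | 86.1% | 87% (Table 1: 87.3%) |

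The plan's figures reproduce.

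**2. Slope distortion in one man (assumed values).** PSAs at −12, −9, −6, −3 and −1 months; true log slope 0.05 per month, so PSADT = 0.693/0.05 = 13.9 months. PSA is suppressed f-fold at −12, half of that on the log scale at −9, and fully released by −6. The values at −6, −3 and −1 give the two rises that item 5 asks for.

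Mean time is −6.2; deviations are −5.8, −2.8, 0.2, 3.2 and 5.2; their sum of squares is 78.8. The excess slope is ln f × (5.8 + 0.5 × 2.8)/78.8 = 0.0914 × ln f.

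| f | Fitted slope | Fitted PSADT (months) | Ratio if on-study slope stays 0.05 |
|---|---|---|---|
| 2 | 0.113 | 6.1 | 2.3 |
| 3 | 0.150 | 4.6 | 3.0 |
| 5 | 0.197 | 3.5 | 3.9 |

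Smaller suppression can also cross the 9-month cut. With 1.5-fold at −12 only, the slope is 0.05 + 0.405 × 5.8/78.8 = 0.080, so PSADT is 8.7 months.

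**3. The 0.10 ng/ml floor.** For f = 5, the −12 value is exp(−0.55)/5 = 0.115 of the −1 value, so it is usable only if the −1 PSA is at least 0.10/0.115 = 0.87 ng/ml. The −9 value is exp(−0.40)/√5 = 0.30 of it, usable from 0.33 ng/ml. Below 0.33 both drop out and the true slope is recovered. Between 0.33 and 0.87 only the −9 value remains. With four points the sum of squares is 36.75 and the excess is 0.805 × 4.25/36.75 = 0.093, so the slope is 0.143 and PSADT 4.8 months. The floor helps at low PSA only.

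**4. A second layout.** Seven PSAs two months apart, with a recovery rise at the start of the window (assumed).

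| True PSADT | Log rise 0.3 over 2 to 6 months | Log rise 0.69 over 2 to 6 months |
|---|---|---|
| 12 months | 9.4 to 8.4 | 7.3 to 6.0 |
| 15 months | 11.1 to 9.7 | 8.3 to 6.7 |

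Not every case crosses the cut; many do.

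**5. Primary analysis.** Suppose 20% (40%) of men carry an excess slope uniform on 0.06 to 0.15, with a true pre-treatment slope SD of 0.05 (all assumed). The mean square of the excess is 0.105² + 0.09²/12 = 0.0117. Added variance is 0.2 × 0.0117 − 0.021² = 0.0019 (0.4 × 0.0117 − 0.042² = 0.0029), against 0.0025. A correlation of 0.30 falls to 0.30 × √(0.0025/0.0044) = 0.23 (0.20). Noncentral-t power moves from 86.1% to 84.8% (84.3%).

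A simulation of 10,000 trials per setting (ρ 0.30, pre-treatment SD 0.075, mean inflation about 0.06) gave, at 0%, 20% and 40% affected, type I error 5.3% each time, mean estimate −0.050 each time, and power 85.4%, 85.5% and 85.2%.

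**6. Within-arm change.** With no treatment effect, the mean log PSADT ratio shifts by the affected share times the log ratio. For 20%: 0.2 × ln 2.27 = 0.16 to 0.2 × ln 3.94 = 0.27, a geometric mean ratio of 1.18 to 1.32. For 40%: 0.33 to 0.55, or 1.39 to 1.73. The shift has the same expectation in both arms.

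**The case against.** The text does not clearly order the use of pre-recovery values. Item 4b says to record them, the sentence in section 11.1 about using all data points follows the on-study slopes, and the data behind the pre-treatment slope can be read as the eligibility PSAs governed by items 3–5. Section 2.3 can be read as a minimum of three recovered values rather than a ban on others. This stands as a description of ambiguity. It does not close the gap, because no sentence excludes the earlier values and two analysts could compute different slopes for the same man.

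The affected group is also narrow: prior hormone therapy, recovery inside the window, PSAs drawn during recovery, and values above the floor. That stands, and the documents give no share.

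A reader might infer four stronger things that the documents do not support.

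- *The primary result is biased.* The slope and stratum are fixed before treatment starts, so the error falls alike on both arms; the primary ANCOVA does not use the strata.
- *The trial is underpowered.* The statement "this study will have 83% power to detect a difference in post-study PSA slope of -0.05" already assumes minimal correlation, and losing the covariate entirely leaves 82.8%.
- *Hormone recovery sets the baseline PSADT.* Item 5 still requires two later rises, and only some men are exposed.
- *Item 5 cannot be verified.* Prior hormone-therapy dates are recorded (calendar note 6), and the registration packet calls for testosterone and PSA results plus other pertinent eligibility records. A dedicated recovery date is missing; source verification is not.

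**Conclusion.** The point holds as a minor one. Section 3.1 items 4–5 and section 11.1 do not carry through the condition that section 2.3 describes. In men whose testosterone recovered inside the window, the pre-treatment slope can be overstated enough to change the PSADT stratum and multiply the PSADT ratio by roughly 2 to 4, under assumed suppression of 2- to 5-fold and PSAs above the floor. The exposed results are the within-arm paired tests and confidence intervals in section 11.2, which could show lengthening in both arms with no treatment effect. The between-arm PSADT ratio test gains noise but no systematic bias. For the primary analysis the cost is at most a point or two of the gain from covariate adjustment, under assumed shares of 20% to 40%. The size of the problem in this trial cannot be stated without the share of men with late recovery and the size of their PSA rebound.

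**What to change.** For men with prior hormone therapy, record the date of the first testosterone that meets the protocol's recovery definition. State in both section 3.1 and section 11.1 that only PSAs drawn on or after that date, with the existing minimum of three, are used for the PSADT stratum and the pre-treatment slope. Reconcile *recovered*, *normal* and the 150 ng/dL screening level into one definition, and reword exclusion 2 so that it has one meaning. This review does not propose the threshold.

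The cost is one sentence in each section and one date field beside the hormone-therapy dates already collected. A few men may need another PSA before entry. The sample size does not change.
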